Overall Study Design. For Aims 1 and 2, a prospective, observational study will recruit 100 men and women with chronic low back pain (+/- leg pain) who are scheduled to undergo lumbar spine surgery at the University of Kansas Medical Center (KUMC). 50 will participate in phenotypic characterization and 50 will participate in phenotypic characterization and quantitative sensory testing (QST) procedures. After screening, informed consent, and enrollment into the study, all subjects will undergo an evaluation which includes a comprehensive battery of questionnaires for patient phenotyping that will assess symptoms including pain, physical function, depression, anxiety, and catastrophizing symptoms. QST parameters will only be performed on half of the cohort of lumbar spine surgery patients. Patient phenotyping and QST procedures will take place in one visit pre-operatively. At two weeks, one month, three months, & six months post-surgery, we will administer one questionnaire to determine analgesic response to surgery. This will establish longitudinally-designated post-surgical analgesic outcome groups (see Statistical Analysis section for definitions). Instead of just a three month time point that is often used in analgesic trials, a six month time point was chosen to give adequate time for recovery and response to surgery. Phenotyping and QST will also be done in a cross-sectional manner on 50 age and sex-matched healthy controls and 50 age and sex-matched patients with an established diagnosis of FBSS (established-FBSS) to compare to the longitudinally-designated post-surgical analgesic outcome groups. For Aim 3, 30 men and women with chronic low back pain (+/- leg pain) who are scheduled to have lumbar spine surgery at KUMC will undergo pre-operative functional, structural, and chemical neuroimaging studies. 15 age and sex-matched healthy controls and 15 age and sex-matched established-FBSS patients will also undergo the same neuroimaging studies to compare to the longitudinally-designated post-surgical analgesic outcome groups. Patients for Aim 3 will be recruited from both the prospective and cross-sectional cohorts enrolled for Aims 1 and 2. The goal of the studies in Aim 3 are to investigate whether pre-operative functional, structural, and chemical neuroimaging findings known to be associated with centralized pain and indicative of CNS amplification are associated with the centralized pain phenotype and possibly predictive of failure to achieve pain relief after lumbar spine surgery. We acknowledge that these studies are exploratory and may be underpowered but feel that they will at a minimum provide critical preliminary data for future studies.

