
C. Sample size, statistical methods, and power calculation

Aim 1 Analyses: To demonstrate that common patient characteristics consistent with a centralized pain phenotype are associated with a patient's failure to derive benefit from lumbar spine surgery. **Analysis**

1a: Analgesic outcomes (AOC) for patients in the prospective cohort will be defined as "AOC-success" or "AOC-failure" for the purposes of further analyses. AOC-success is defined as those who demonstrate a 50% reduction in pain scores from baseline to 6 months, which would be a response more commensurate with the invasiveness of the intervention of spine surgery than a minimal clinically important difference score (MCID). FMness as measured by the 2011 FM Survey Criteria score⁶⁶ is the primary measure of interest and will be split by median score (and defined as FM-high and FM-low). Differences in surgical failure proportions (determined by pain score change as described above at 6-months) between the FM-high (n=50) and FM-low (n=50) groups will be tested using a two-sided chi-squared statistic at $\alpha=.05$. In addition to FMness, differences between AOC-success and AOC-failure groups for each of the constructs contained under the subheading "Comprehensive Phenotyping Battery" will be examined using appropriate parametric or non-parametric analyses. Furthermore, we wish to explore how multiple patient characteristics vary across these cohorts. A stepwise logistic regression model will then be fit to evaluate multivariate relationships. The analyses conducted in this aim will provide the candidate an opportunity to learn multivariate data analysis with advanced regression modeling as well as more familiarity with patient reported outcome measures. **Analysis 1b:**

Phenotypic differences between the AOC-failure group and the established-FBSS group will be examined using appropriate parametric or non-parametric tests to see if the longitudinally designated AOC-failure cohort is phenotypically similar in nature to the cross-sectional established-FBSS patients. We hypothesize that AOC-failure patients will appear similar to established-FBSS patients. The same comparisons will be explored for the longitudinally designated AOC-success group compared to the cross-sectional healthy controls group.

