Sample size for Study Procedures in Aims 1 and 2: We anticipate screening approximately 60 pre-operative lumbar spine surgery patients per year for possible enrollment into the study. Assuming a 50-60% recruitment rate, we estimate approximately 30-35 lumbar spine surgery patients enrolled per year during Years 1-4 of the award. This leads to an estimated total sample size of 100 lumbar spine surgery patients. We will also aim to recruit and enroll equal distributions of established-FBSS patients (n=50) and healthy controls (n=50). For the assumed effect size (population of 0.10 vs 0.50) and sample sizes (50 and 50 based on 2011 FM Survey Criteria score median split) and $\alpha=.05$ (two-sided) the power is 0.99. Several different assumptions were also explored. For example, if the assumed effect size is (population of 0.15 vs 0.45) or (population of 0.17 vs 0.43), then the respective power calculations are 92% and 82%, both which are adequate for significance purposes (e.g., >80%). The larger sample size will also be important for exploring multivariate models and potential subgroup analyses. The inclusion of healthy controls and established-FBSS patients will ensure adequate matching of gender and age to the patient cohorts for analyses.

Sample size for Study Procedures in Aim 3: We aim to recruit 30 lumbar spine surgery patients, 15 healthy controls, and 15 established-FBSS patients out of the total cohort to participate in the

neuroimaging study procedures. As this study is powered for the primary hypothesis in Aim 1, issues of power are of less concern for these investigatory neuroimaging studies.

D. Subject Criteria (See Vulnerable Populations appendix, if applicable):

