Comprehensive Patient Phenotyping: This battery of questionnaires is intended to understand key aspects of pain, mood, and function as quickly and efficiently as possible. The focus of these measures are on obtaining an accurate assessment of pain, while also asking about physical function, anxiety, depression, and other associated somatic disturbances. [name] and other CPFRC researchers have been instrumental in developing this protocol of questionnaires. On average, the battery of questionnaires used for phenotyping take anywhere from 10 minutes to 60 minutes to complete depending on study visit.

- *Demographics:* Sex, age, race/ethnicity, marital status, education level, family history of pain, and body mass index (BMI) will be assessed in the context of standardized case report forms. Sex is an important biologic variable to investigate as centralized pain is more common in females, and is probably largely responsible for the fact that nearly any chronic pain condition is 1.5 – 2 times more common in women than in men.¹⁴²
- *Fibromyalgia-ness (FMness):* FMness is a measure of pain and co-morbid symptom extensiveness and severity. It is calculated by combining the scores from the Widespread Pain Index with the Symptom Severity Scale from the 2011 FM Survey⁶⁶ to derive a continuous metric purportedly indicative of the degree of CNS pain amplification present in a given individual.⁶⁷
- *Early Life Trauma History.* Trauma history will be assessed using The Childhood Traumatic Events Scale (CTES).¹⁴³ This scale assesses not only for physical and sexual abuse but also other

forms of early trauma such as a prolonged childhood illness, neglect, or death of a parent. Early life trauma is hypothesized to be associated with the top-down variant of centralization.

- *Clinical Pain*: Pain severity (worst, least, average, and current) due to pain will be assessed using the *Brief Pain Inventory (BPI)*. The *BPI* is validated for chronic, non-malignant forms of pain, and asks patients to rate their current pain intensity, as well as their worst, least and average pain in the 7 days (0-10 NRS) and has been recommended by IMMPACT as a measure of choice for the assessment of pain in clinical research.¹⁴⁴⁻¹⁴⁶
- *Neuropathic Pain Descriptors*: The *PainDETECT* is a 9-item measure of sensory descriptors and spatial and temporal characteristics that has demonstrated utility in identifying central neuropathic pain.¹⁴⁷

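### Age and sex matching to the surgery cohort does not guarantee balance with the AOC-success and AOC-failure groups actually compared, and no adjustment is specified

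*Combined protocol and SAP*

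**What the plan says.** Section II.B (Overall Study Design) plans 50 healthy controls and 50 established-FBSS patients, both described as matched on age and sex, "to compare to the longitudinally-designated post-surgical analgesic outcome groups". Section II.C (Sample size for Aims 1 and 2) adds that "The inclusion of healthy controls and established-FBSS patients will ensure adequate matching of gender and age to the patient cohorts for analyses". The target is given only as the patient cohorts. Neither section says whether that means all 100 surgery patients, the 50 with QST or an outcome group, whether matching is individual or by frequency, or when comparators are enrolled.

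Outcome status is fixed by the change in pain from baseline to 6 months (II.C, Analysis 1a). For Analysis 1b, "Phenotypic differences between the AOC-failure group and the established-FBSS group will be examined using appropriate parametric or non-parametric tests", and the same is planned for AOC-success against healthy controls. Aim 2 reuses the Aim 1 analyses for the QST measures; its counterpart is called 2b here, after Hypothesis 2b. No covariate is named for these contrasts. The only multivariable model, a stepwise logistic regression, sits under Analysis 1a and forces in neither age nor sex.

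**The concern.** The plan claims comparability on age and sex for its analyses, but the groups analysed are subsets of the cohort. Matching at cohort level carries over to a subset only if the variable that forms the subset is unrelated to the matching factors. The plan's own premises make that doubtful for sex. Section II.E (Demographics) says that "centralized pain is more common in females", and the overall hypothesis is that centralized pain contributes to surgical failure. If both hold, the failure group contains more women than the cohort.

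Hypotheses 1b and 2b predict similarity: failures should resemble established FBSS, and successes should resemble healthy controls. A difference in sex or age mix would shift pain thresholds, FM scores and symptom measures for reasons unrelated to surgical outcome. It could add to or subtract from the difference on which those hypotheses are judged.

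**Working it through.** **Inputs from the documents**
- Analysis 1a: failure proportions "tested using a two-sided chi-squared statistic" at two-sided alpha 0.05, with groups of "50 and 50 based on 2011 FM Survey Criteria score median split" (II.C).
- Failure proportions: "population of 0.10 vs 0.50", "population of 0.15 vs 0.45", and 0.17 vs 0.43 (II.C). Each pair averages 0.30.
- Comparators: 50 and 50 (II.B). Surgery patients with QST: 50 (II.E).
- Roughly equal numbers of men and women in each cohort (II.D).
- Failure range quoted in the Background: 10-40%.

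**Assumptions**
- Both comparator groups are 50% women.
- The failure risk ratio r, women to men, is 1, 1.5 or 2. The values 1.5 and 2 are borrowed from the sex ratio for the prevalence of chronic pain conditions in II.E. The documents give no sex ratio for surgical failure.
- The sex effect d on a measure is 0.3 to 0.8 SD.

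**1. The plan's own figures.** Power = Φ{[|p2−p1| − 1.96√(2p̄(1−p̄)/50)] / √[(p1(1−p1)+p2(1−p2))/50]}. With p̄ = 0.30 this gives 0.996, 0.918 and 0.820, which reproduces the stated 0.99, 92% and 82%. These are the only power figures given, and none concerns 1b or 2b.

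**2. Group sizes.** 0.30 × 100 = 30 failures and 70 successes. In the QST half, 0.30 × 50 = 15 and 35. Over 10-40% failure, the failures number 10-40 of 100, or 5-20 of 50. Fifty controls cannot be paired one to one with 70 successes.

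**3. Sex mix after the split.** Women among failures = r/(1+r). Women among successes = [0.5 − 0.30·r/(1+r)]/0.70.

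| r | Women in AOC-failure | Gap to FBSS | Women in AOC-success | Gap to controls |
|---|---|---|---|---|
| 1 | 50% | 0 | 50% | 0 |
| 1.5 | 60.0% | +10.0 points | 45.7% | −4.3 points |
| 2 | 66.7% | +16.7 points | 42.9% | −7.1 points |

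The failure column does not depend on the overall failure rate. The success gap runs from 1 point (10% failure, r = 1.5) to 11 points (40% failure, r = 2).

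**4. Chance alone (r = 1, hypergeometric).** With 30 failures drawn from 50 women and 50 men, the 95% range is 37-63% women, and a gap of 10 points or more has probability 0.28. With 15 failures from 25 and 25, the range is 27-73% and the probability 0.54.

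**5. Bias from sex.** Bias = gap × d.
- Failure vs FBSS: 0.10 × 0.3 = 0.03 SD to 0.167 × 0.8 = 0.13 SD.
- Success vs controls: 0.043 × 0.3 = 0.01 SD to 0.071 × 0.8 = 0.06 SD.

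With SE = √(1/n1+1/n2), the chance that a nominal 5% test declares a difference when the sex-adjusted difference is zero is 5.2-8.9% for 30 vs 50 and 5.1-6.1% for 70 vs 50. In the QST half it is 5.1-7.4% (15 vs 50) and 5.0-5.8% (35 vs 50).

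**6. Cost of adjusting for sex.** Variance inflation = 1/(1−R²), where R² = w1·w2·gap²/[q(1−q)], w1 and w2 are the two groups' shares of the pooled sample, and q is the pooled share of women. For 30 vs 50 at a gap of 0.167, R² = 0.375 × 0.625 × 0.0278 / (0.5625 × 0.4375) = 0.0265, so the inflation is 1.027. The difference detectable with 80% power moves as follows:
- 30 vs 50: 0.647 to at most 0.656 SD.
- 70 vs 50: 0.519 to 0.520 SD.
- 15 vs 50: 0.825 to at most 0.833 SD.
- 35 vs 50: 0.617 to 0.619 SD.

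Neither the bias nor the inflation from age can be computed, because the documents give no age distribution.

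**The case against.** **Timing.** A reader might infer that comparators are enrolled and matched before any outcome is known. The documents do not say so. Surgery enrolment runs over several years, comparators attend once, and later matching is not excluded. That stands. Cohort-level matching is still the better-supported reading. Comparator numbers are fixed at 50 and 50, sex balance is set per cohort, and V.B ends the study when the last surgery patient completes the 6-month visit, so the full outcome groups exist only then.

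**Unmatched and unadjusted.** A reader might also infer that the comparisons are unmatched and that adjustment is ruled out. Neither is supported. If age and sex do not predict failure, the subsets stay balanced in expectation. The wording of Analysis 1b neither names nor excludes a covariate model. What can be said is that balance is not guaranteed and adjustment is not specified.

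**Size.** The 1.5-2 ratio is borrowed, no section says that failure differs by sex or age, and the bias is small even with that ratio. For success versus controls, the selection of controls (FM score of 3 or less, pain below 3/10) probably matters more than a 4-7 point sex gap. A chance imbalance is not a systematic bias; it affects how one data set is read. All of this stands and limits the weight of the point.

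**Question asked.** Whether groups look alike is partly a descriptive question, and adjustment changes the quantity estimated. This is a good reason to report both results, but not to leave adjustment unspecified when the plan itself wants groups comparable on age and sex.

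**Conclusion.** The point holds in limited form. The design does not secure age and sex comparability for the 1b and 2b contrasts, and the plan names no analysis that would restore it. Under the stated assumptions the sex gap is 10-17 points for failure versus FBSS and 4-7 points for success versus controls, with bias of 0.03-0.13 SD and 0.01-0.06 SD. At a ratio of 1 the expected gap is zero, although chance gaps of 10 points or more in the failure group remain common, especially in the QST half. Any age imbalance would add an amount that cannot be sized.

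It would be too strong to conclude that these contrasts are invalid or that sex imbalance by itself would decide Hypotheses 1b and 2b; the figures do not show that. Nor does the point reach the main result: Analysis 1a uses no controls or FBSS patients, and its stated power stands. This is an inexpensive improvement to secondary comparisons and is worth making.

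**What to change.** 1. Analyse each 1b and 2b contrast with a linear model, or a rank or ordinal equivalent, containing group, age and sex. Report the adjusted difference beside the unadjusted one.
2. Reword the matching sentence in II.C to say that comparators are matched to the surgery cohort as a whole, and that residual imbalance with the outcome groups is handled by adjustment. State the matching method and timing there. If another target was intended, say which.
3. Tabulate age and sex for AOC-success, AOC-failure, FBSS and controls.

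This is a wording change. Age and sex are already collected on everyone, and no new data or participants are needed. The cost is about two degrees of freedom in contrasts of about 30 vs 50 and 70 vs 50 (15 vs 50 and 35 vs 50 for QST), plus variance inflation of at most about 3% from sex under the assumptions above. The inflation from age is unknown.

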to accurately "phenotype" lumbar spine surgery patients for relevant trait and state constructs associated with centralized pain. *Hypothesis 1a: Pre-operative patient characteristics associated with a centralized pain phenotype will be associated with and potentially predict a patient's failure to derive benefit from surgery intended to treat chronic pain. Hypothesis 1b: Patients who fail to obtain pain relief from lumbar spine surgery in a longitudinal cohort will appear phenotypically similar to a cross-sectional cohort of established-FBSS patients and those who do obtain pain relief from lumbar spine surgery will appear phenotypically similar (except for back pain) to healthy controls.*

Aim 2: To confirm that altered pain processing mechanisms consistent with centralized pain are seen in patients who have failed to respond to lumbar spine surgery. In order to accomplish this aim, the candidate will learn how to perform and analyze the results of quantitative sensory testing (QST) (detecting pain thresholds, testing the integrity of descending analgesic pathways, and temporal summation). *Hypothesis 2a: Pre-operative altered pain processing mechanisms consistent with centralized pain will be associated with and potentially predict a patient's failure to derive benefit from surgery intended to treat chronic pain. Hypothesis 2b: Patients who fail to obtain pain relief from lumbar spine surgery in a longitudinal cohort will have augmented QST changes similar to a cross-sectional cohort of established-FBSS patients and those who do obtain pain relief from lumbar spine surgery will have QST changes similar to healthy controls.*

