Inclusion (ALL) 
 • Able to Read and Speak English • Between 22-70 years old • Stable dose (or not on) of adjunctive pain medications for at least 2 weeks prior to QST • Able to provide informed consent 	Exclusion (ALL) 
 • Diagnosis of a medical condition that isn't minor or stable • Current litigation regarding a medical illness • Drug or alcohol abuse • Severe physical impairment • Co-morbid medical conditions that may impair physical functional status • Psychiatric condition that may impair functional status (active psychosis or suicidal ideation) • Pregnant or nursing • Liver failure, cirrhosis, hepatitis • Severe cardiovascular disease
Inclusion (ALL) QST 
 • Right-Handed • Willingness to refrain from alcohol and nicotine on the day of QST • Willingness to refrain from pain meds 12 hours prior to QST 	Exclusion (ALL) QST 
 • Current or recent (6 months) use of artificial fingernails or nail enhancements • Neuropathy or loss of feeling in upper or lower extremities

 Willingness to refrain from strenuous exercise that would cause muscle or joint soreness 48 hours prior to QST 	
Inclusion (Healthy) In addition to (ALL) above: n/a	Exclusion (Healthy) In addition to (ALL) above: 
 Diagnosis of a chronic pain syndrome (mild is fine; but less than 3/10 pain score on any body region) Score >3 on FM 2011 survey
Inclusion (FBSS) In addition to (ALL) above: 
 Has chronic low back pain (+/- leg pain) for > 6 months after a lumbar spine surgery Low back pain severity greater than or equal to 4/10 	Exclusion (FBSS) In addition to (ALL) above: 
 Involved in litigation for low back pain or previous low back surgery
Inclusion (LSS) In addition to (ALL) above: 
 Low back pain severity greater than or equal to 4/10 Willingness to participate in longitudinal follow-up questionnaires post-op 	Exclusion (LSS) In addition to (ALL) above: 
 Involved in litigation for low back pain or previous low back surgery History of a previous back surgery LSS is due to spinal cancer-related diagnoses LSS is urgent or emergent

Eligibility (MRI): In addition to eligibility within each group

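### Healthy controls are capped at an FM score of 3, so the exploratory comparison of AOC-success patients with them on FMness (Analysis 1b) is biased toward a difference

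*Combined protocol and SAP*

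**What the plan says.** **Controls.** The eligibility table in Section II.D.1 excludes healthy volunteers for a "Score >3 on FM 2011 survey". It also excludes a chronic pain diagnosis, with the gloss "mild is fine; but less than 3/10 pain score on any body region". The withdrawal rule after the MRI criteria removes anyone who later shows an exclusion criterion for their cohort.

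**Surgery patients.** They must have "Low back pain severity greater than or equal to 4/10". No FM limit is listed for them.

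**Measure.** The phenotyping section of II.E states that "FMness is a measure of pain and co-morbid symptom extensiveness and severity", and builds the score from the Widespread Pain Index and the Symptom Severity Scale. The study schedule gives the FM survey to all cohorts at baseline, and again to surgery patients at 1, 3 and 6 months.

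**Comparison.** Hypothesis 1b predicts that "those who do obtain pain relief from lumbar spine surgery will appear phenotypically similar (except for back pain) to healthy controls". In Section II.C, Analysis 1b first sets AOC-failure patients against established-FBSS patients on phenotype, then adds: "The same comparisons will be explored for the longitudinally designated AOC-success group compared to the cross-sectional healthy controls group". Responder status depends on pain alone: "AOC-success is defined as those who demonstrate a 50% reduction in pain scores from baseline to 6 months". Nothing in the plan exempts FMness from this comparison, adjusts for the cap, or mentions it.

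**The concern.** Screening controls tightly is a reasonable choice when the aim is to show a contrast. Here the hypothesis is similarity, and one of the two groups has had its upper scores removed on the variable that is compared. The control distribution of FM scores is then partly set by the eligibility rule and does not estimate what healthy people score. A significant gap could arise because responders keep centralized-pain features, or only because controls scoring 4 or more were turned away, and the test cannot tell these apart.

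The study is meant to supply preliminary data for a larger grant application. A gap produced by selection could be carried forward as evidence that even patients who did well after surgery remain unlike healthy people on the study's marker of centralized pain.

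**Working it through.** **1. The plan's own figures.** No power or sample size is given for the responder-versus-control comparison. The figures that are given concern Analysis 1a (50 vs 50, two-sided chi-squared, α = 0.05). With p̄ = 0.30 in all three cases,

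power = Φ{ [|p₁ − p₂| − 1.96·√(2·p̄(1 − p̄)/50)] / √(p₁(1 − p₁)/50 + p₂(1 − p₂)/50) }, where 1.96·√(2·0.21/50) = 0.1796.

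- 0.10 vs 0.50: Φ[(0.40 − 0.1796)/0.0825] = 0.996 (plan: 0.99)
- 0.15 vs 0.45: Φ[(0.30 − 0.1796)/0.0866] = 0.918 (plan: 92%)
- 0.17 vs 0.43: Φ[(0.26 − 0.1796)/0.0879] = 0.820 (plan: 82%)

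The plan's power figures reproduce. They do not depend on the control cap.

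**2. Inputs for the comparison at issue.**

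- Control scores 0–3 (II.D.1); 50 controls (II.C).
- Responders: 100 × (1 − 0.30) = 70, using the average failure rate implied by each of the three pairs above, with no dropout.
- Tests: Analysis 1b leaves the choice between parametric and non-parametric tests open, so Welch t and Mann-Whitney are both shown, two-sided at 5%. The level is an assumption, because the plan states α only for 1a.
- FM distribution: assumed. The only observed FM mean in the documents is 13.7, in 35 pilot FBSS patients, who belong to neither group. A negative binomial is used, with p = mean/SD² and r = mean·p/(1 − p), over means 1.5–10 and SDs 1.6–5.
- The score analysed for controls is assumed to be subject to the cap.

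**3. One case by hand (mean 3, SD 3).** p = 3/9 = 1/3 and r = 1.5. The probabilities of scores 0, 1, 2 and 3 are 0.1925, 0.1925, 0.1604 and 0.1247, which sum to 0.670. The mean of capped controls is (0.1925 + 2 × 0.1604 + 3 × 0.1247)/0.670 = 1.32. Their variance is (0.1925 + 4 × 0.1604 + 9 × 0.1247)/0.670 − 1.32² ≈ 1.17. The cap alone creates a gap of 3 − 1.32 = 1.68. Its standard error is √(9/70 + 1.17/50) = 0.39, so z ≈ 4.3 and the chance of a significant result is about Φ(4.3 − 1.96) = 0.99, although the source populations are identical.

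**4. Simulation.** Responders and controls come from the same distribution, so the correct rejection rate is 5% (1,000 runs per row; Mann-Whitney / Welch t).

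| Source mean (SD) | Share scoring 0–3 | Mean of capped controls | Rejection, no cap | Rejection, cap at 3 |
|---|---|---|---|---|
| 1.5 (1.6) | 89% | 1.08 | 3.8% / 4.0% | 17% / 40% |
| 2 (2) | 81% | 1.23 | 4.4% / 4.9% | 42% / 78% |
| 3 (3) | 67% | 1.33 | 4.5% / 4.0% | 91% / 99.9% |
| 4 (3.5) | 54% | 1.54 | 4.0% / 5.9% | 99.7% / 100% |
| 6 (4) | 30% | 1.95 | 4.5% / 4.3% | 100% / 100% |
| 10 (5) | 7% | 2.33 | 4.3% / 4.1% | 100% / 100% |

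A repeat gave 18% / 39%, 42% / 79% and 89% / 99.9% at means 1.5, 2 and 3, over 99% at means 4 and 6, and about 4–7% without the cap.

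**The case against.** **The choice of controls is defensible.** The plan treats the FM score as a surrogate for centralized pain that predicts outcome well below the diagnostic threshold, so a reference group low on that construct is coherent. The bias also runs against Hypothesis 1b and cannot manufacture similarity. Both points stand. They justify keeping the control group, but not testing FMness against it.

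**The stakes are limited.** A reader might infer that the primary analysis is damaged, because FMness is the main measure of interest. That label belongs to Analysis 1a, which compares failure proportions between FM-high and FM-low patients within the surgery cohort. The affected item is one measure in one half of an exploratory comparison, in a study that describes itself as generating data for later work.

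**The result is not settled in advance.** A reader might infer that similarity on FMness must be rejected whatever surgery achieves. That would need typical responder scores clearly above 3, and the documents do not give them. Analysis 1b also does not say whether the surgery patients' baseline or 6-month score is used. If scores run low, the cap biases the comparison without determining it.

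**Assumed group differences do not size the defect.** A reader might assume responder means of 5–8 (SD 3.5–5) and note that capped controls would almost always differ. Uncapped controls with an assumed mean of 3 and SD of 3 would usually differ too: the standardised differences are 0.61–1.41, with power from 0.91 upward at 70 vs 50. Only the equal-source calculation isolates the cap.

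**The controls are not symptom-free.** Mild pain, FM scores of 1–3, and stable anxiety or depression are all allowed.

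**Spill-over is plausible but unquantified.** The documents give no correlation between FM score and the other scales or QST, and only 50 surgery patients have QST, so the 70 vs 50 figures do not carry over to it.

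**Conclusion.** The concern holds for FMness and its two components in the AOC-success versus healthy-control half of Analysis 1b. If responders truly share the FM distribution of otherwise eligible healthy people, the planned test declares a difference far more often than 5% of the time: several-fold more often at the lowest source means examined, and nearly always from a mean of 3 upward.

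These rates rest on an assumed negative binomial shape, assumed means and SDs, 70 responders with complete data, and a capped score being the one analysed. The direction of the bias does not depend on the assumed shape, provided some otherwise eligible volunteers score above 3; its size does. The AOC-failure versus established-FBSS comparison is unaffected, as is Analysis 1a. For other battery scales and QST, the documents support a caution about interpretation and no stated amount of bias.

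**What to change.** Add to Analysis 1b in Section II.C, for example:

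> The 2011 FM Survey score, the Widespread Pain Index and the Symptom Severity Scale will be described, but not tested, between AOC-success patients and healthy controls, because controls were selected to have an FM score of 3 or below. Differences on battery or QST measures correlated with the FM score may partly reflect this selection.

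Repeat the disclosure wherever these results are reported.

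The cost is a short addition to the plan and the loss of a formal test against controls for one battery measure. No change to eligibility is proposed. Lifting the cap during enrolment would mix truncated and untruncated controls, and the remaining pain exclusion would still select on symptoms that feed the Widespread Pain Index.
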